5.5.2.3. Combined analysis of solicited and unsolicited AEs

The combined analysis of solicited and unsolicited AEs will be performed on the Overall safety set.

Solicited AEs will be coded by MedDRA as per the following codes:

Solicited symptom	Preferred Term code	Corresponding Preferred Term decode
Pain	10022086	Injection site pain
Redness	10022061	Injection site erythema
Swelling	10053425	Injection site swelling
Headache	10019211	Headache
Fatigue	10016256	Fatigue
Nausea	10028813	Nausea
Vomiting	10047700	Vomiting
Diarrhoea	10012727	Diarrhea
Abdominal pain	10000081	Abdominal pain
Myalgia	10028411	Myalgia
Shivering	10008531	Chills
Fever	10037660	Pyrexia

Table 9Solicited AE with Preferred Term

5.5.2.4. Other safety analyses

Medications will be coded using WHODRUG dictionary.

All collected concomitant medications and vaccinations will be listed. In addition, prior and concomitant vaccinations will be summarized. In case of pregnancies during the study, follow-up data and pregnancy outcomes will be described in detail.

For all subjects in each group and each haematology and biochemistry parameter:

- The percentage of subjects having haematology and biochemistry results below or above the local laboratory normal ranges will be tabulated as post-vaccination versus pre-vaccination values: Visit 2 versus screening, for all groups of the safety lead-in; Visit 2 versus Visit 1 for group 5 Step 1 of the PoP; Visit 5 versus Visit 4, for group 4 of the safety lead-in, and Visit 6 versus Visit 5, for group 5 Step 1 of the PoP.
- Post-vaccination versus pre-vaccination values (Visit 2 versus screening, for all groups of the safety lead-in; Visit 2 versus Visit 1 for group 5 Step 1 of the PoP; Visit 5 versus Visit 4, for group 4 of the safety lead-in, and Visit 6 versus Visit 5, for group 5 Step 1 of the PoP) will be tabulated according to FDA Guidance for Industry "Toxicity Grading Scale for Healthy Adult and Adolescent Volunteers Enrolled in Preventive Vaccine Clinical Trials", see section 10.3.

5.5.2.5. Exclusion of implausible solicited Adverse Event

Some local and general adverse events will be directly measured by the subject and will not be subject to a reconciliation process with the exception of redness and swelling over 300 mm, which will be subjected to check and reconciliation.

The plausible measurements programmed in the eDiary are summarized in the table below:

Parameter	Plausible range measurements
Body temperature	33.1°-41.9°
Redness	1 mm899 mm
Swelling	1 mm—499 mm

Table 10 Plausible Solicited Adverse Events

6. ANALYSIS INTERPRETATION

Except for analysis on efficacy objectives, with predefined success criteria and an appropriate type I error control, comparative analyses are descriptive with the aim to characterize the difference between groups.

With respect to confirmatory analyses on efficacy objectives the interpretation will be done in a hierarchical manner.

After the final analysis for the first hypothesis a sequential procedure will be used in order to control the overall type I error for the efficacy objective: starting from the first

208833 (STAPH AUREUS BIOCONJ-001 STG) Statistical Analysis Plan Amendment 5

hypothesis on the efficacy after the second dose, the second hypothesis on the efficacy after the first dose will be tested only if the efficacy after two doses will be demonstrated.

Figure 4 Sequence for evaluating both efficacy objectives in order to control the overall type I error below 7.5% (one-sided) and the power equal to 80%

*All subjects who experience an SSTI recurrence at least two weeks after the second dose. If a subject experiences an event after the first and before the second dose the case will be not considered as first event after the second dose. If a subject has an event after the first and another after the second dose, only the case after the second dose will be considered as first event after the second dose.

**The adjusted alpha for this hypothesis can only be given at the time of analysis as the adjustment is dependent on the alpha spent at the interim analysis.

***All subjects who experience an SSTI recurrence at least two weeks after the first dose.

7. CONDUCT OF ANALYSES

7.1. Sequence of analyses

The final study report will contain at least the final analyses of all primary and secondary endpoints. If the data for tertiary endpoints become available at a later stage, (an) additional analysis/ analyses will be performed. These analyses will be documented in annex(es) to the study report.

All analyses (including interim analysis) will be conducted on clean data.

• The analyses will be performed stepwise: An interim analysis for efficacy and futility will be done when 48% of the assumed total number of culture confirmed cases of recurrent *S. aureus* SSTIs (13 events after the second dose) will be observed. The timing of the interim analysis will be according to how the data actually accrued. This analysis will be performed by an independent data analysis centre (IDAC), in order to maintain the blind to the treatment codes. An independent GSK statistician will validate the outcome of the interim analysis provided by IDAC, to check whether efficacy/futility criteria are met (more details in section 7.3)

- The main efficacy analysis and the respective conclusions on efficacy will be done on the total number of events, i.e. at 27 events after the second dose, and the enrolment is stopped. If the enrolment is stopped for efficacy or futility following the interim analysis and we do not observe planned number of 27 events by end of study (Last Subject Last Visit), we proceed to the analysis with all collected number of events.
- A second line efficacy analysis will be performed on all available efficacy data obtained up to study conclusion (1 year of follow up after the second vaccination) but this additional data (beyond 27 events) will not be taken into account for the conclusion of vaccine efficacy. The final clinical study report containing all data will be written and made available to the investigators.

Description	Disclosure Purpose
Interim analysis for efficacy and futility	Internal
Final Analysis for safety and efficacy	Public disclosure, Study report
Annex for efficacy and safety (and other tertiary	Additional efficacy analysis with additional events and
endpoints)	safety

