# 10. STATISTICAL CONSIDERATIONS

## 10.1. Sample size determination

#### 10.1.1. Hypotheses related to primary and secondary objectives

For the primary safety objective no statistical hypotheses are applicable.

Two statistical hypotheses will be tested for the secondary efficacy objective.

- 1. Null Hypothesis : Hazard Ratio (HR) ≥1 after the second vaccination Alternative Hypothesis: HR <1
- 2. Null Hypothesis : Hazard Ratio (HR) ≥1 after the first vaccination Alternative Hypothesis: HR <1

If the first hypothesis is statistically significant, also the second hypothesis will be tested in a sequential procedure. In case the first hypothesis is not significant no conclusions will be taken with respect to the second hypothesis. Both hypotheses will be tested using the log rank test.

For the first hypothesis referring to the key efficacy endpoint two sequential analyses will be done following a Group Sequential Design using the O'Brien-Fleming spending function (with 48% and 100% of the total planned events). *(Amended 6 October 2022)* 

At the interim analysis the first hypothesis will be tested spending 1.61% alpha and 8.83% beta (this means a power equal to about 91%). At the final analysis the alpha will be 5.89% and the beta 11.17% (this means a power equal to about 89%). Overall after two sequential analyses the cumulative alpha will be 7.5% and the cumulative beta 20% (or power equal to 80%).

The assumptions to test the first hypothesis on the HR after the second vaccination are:

- to observe an HR (hazard ratio) equal or below to 0.39
- a true incidence rate for the SSTI equal to 0.07 (starting to count the events two weeks after the second dose)
- time to event follows an exponential distribution.

The second hypothesis of the secondary vaccine efficacy objective will be tested for all the events occurring after the first vaccination, with one-sided alpha equal to 5.89% and power 89% (both adjusted error values will be retrieved from the second group sequential test performed on the first hypothesis).

The following assumptions are made to test the hypothesis on the HR after the first dose of vaccine/placebo:

- to observe an HR below 0.43
- a true incidence rate equal to 0.12 (starting to count the events two weeks after the first dose)
- time to event follows an exponential distribution

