## 10.1.2. Sample size calculation

The incidence rates of *S. aureus* SSTI (index cases and recurrences) at the selected study centre(s) are difficult to predict. For this reason, the study is designed as an event driven trial and includes **CO**. After the dose-escalation safety lead-in epoch and the PoP staggered enrolment step of PoP vaccination epoch are concluded and no safety issues are found, enrolment will continue with a randomisation of 1:1 ratio either to the *S. aureus* candidate vaccine or to the placebo group. It is estimated that approximately 500 to 600 subjects will be needed to achieve the **CO** 

The key objective of clinical efficacy will be measured counting culture confirmed cases of recurrent *S. aureus* SSTIs occurring from 14 days after the second dose up to 12 months after the second dose. Before the second dose has elicited a proper response (i.e. from Day 61 to Day 75) subjects will be also monitored for SSTI.

The event driven design includes **CCL** (culture confirmed *S. aureus* SSTI recurrences) overall after the second dose to test the null hypothesis of no efficacy assuming an HR equal to 0.39 from Day 75 (14 days after the second vaccination) up to 12 months after the second vaccination.

The study sample size is not fixed and the enrolment will proceed until reaching the planned number of events necessary to evaluate the first statistical hypothesis of no efficacy (HR $\geq$ 1) with an overall power equal to 80% and an overall one-sided alpha equal to 7.5%.

A group sequential design with the O'Brien Fleming spending function is applied to the first hypothesis after the second vaccination, CCL

After the final analysis for the first hypothesis a sequential procedure will be used in order to control the overall type I error for the efficacy objective: starting from the first hypothesis on the efficacy after the second dose, the second hypothesis on the efficacy after the first dose will be tested only if the efficacy after two doses will be demonstrated.

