5.3. Efficacy/Effectiveness

5.3.1. Analysis of efficacy planned in the protocol

The efficacy analysis will be based on the mFAS. A supplementary analysis will be based on the PPS.

Rules for SSTI cases:

- All cases of SSTI will be reported, including multiple cases in the same subject.
- The start date of a case is the date of the visit during which the diagnosis is done by a treating physician or equivalent licensed medical professional or based on medical records review by a study physician.

• A new SSTI episode may be assessed by a study physician at site for any SSTI visit occurring after the clinical resolution of the previous SSTI and, if it does not represent a persistence of the previous episode as per medical judgement, it can be considered a new episode.

Endpoint	Statistical Analysis Methods
Key secondary	The analysis of efficacy will be based on the occurrence of the first case of SSTI anytime from 14 Days after the administration of the second dose of the study vaccine up to 12 months. All subjects from the mFAS will contribute to the comparison between the treatment and the placebo groups.
	Time to occurrence of key secondary endpoint during the defined efficacy follow-up period will be compared between groups by calculating the respective Hazard ratio
	Vaccine (VE) will be defined as 1 minus the hazard ratio times 100:
	$VE = (1 - hazard ratio) \times 100$
	Censoring will occur at the time of the last scheduled or medically attended visit without the occurrence of SSTI cases before the end of follow up. Subjects who will complete the follow up without events will be censored at 1 year.
	In order to check the statistical significance, 1-sided P-value for the log rank test will be calculated. 1-sided nominal type I error will be 1.61% at the interim analysis and 5.89% at the final analysis. The objective will be met if the 1-sided P-value calculated for the null hypothesis H0 = [occurrence SSTI VE = 0%] is lower than defined 1-sided alpha level.
Co- secondary	The co-secondary endpoint will be analysed only if the statistical significance is demonstrated for the key secondary endpoint.
	For this analysis, the FAS will account for the first case of SSTI anytime from 14 Days after the administration of the first dose of the study vaccine up to 14 months.

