7.2. Statistical considerations for interim analyses

One interim analysis for efficacy and futility will be done following a group sequential design for the key secondary efficacy analysis. The interim analysis is event driven and is planned when 48% of the assumed total number of culture confirmed cases of recurrent *S. aureus* SSTIs (13 events after the second vaccination) will be observed and it may stop the enrolment of the study for efficacy or futility.

In case of stopping for efficacy at the interim analysis, also the second secondary efficacy endpoint will be tested with the same alpha used for the first hypothesis (alpha=1.613%). Enrolment maybe stopped if the null hypothesis is rejected (efficacy) or accepted (futility) after the interim analysis, but the follow up of subjects will continue for 12 months after the second dose.

The design assumes that 2 sequential tests are made for the key efficacy objective using test boundaries (binding for efficacy and not binding for futility) calculated by the O'Brien-Fleming spending function and assuming that time to event follows an exponential distribution. An adjusted alpha equal to 1.613 % and a beta equal to 8.83% (or a power equal to 91%) will be spent at the interim to reject or accept the null hypothesis for the key efficacy objective with a sample of 13 cases. At the final analysis the adjusted alpha and beta will be, respectively, 5.89% and 11.17% (or a power equal to 89%) with a sample of 27 cases. The final alpha and beta after the two sequential tests will be kept to 7.5% and 20%. The secondary efficacy endpoint will be tested at the final analysis after rejecting the null hypothesis for the key objective.

The proc SEQDESIGN is used for the planning of the test boundaries with the code reported in the section 5.3. The output with the limits is used in the proc SEQTEST (see section 5.3.2)

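### SAP 7.1 does not say that an interim efficacy rejection stands, and so conflicts with SAP 7.2 and Table 5 on which analysis decides the key hypothesis

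*SAP*

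**What the plan says.** **Passages that make the interim decisive.** SAP 7.2 describes the boundaries as "binding for efficacy and not binding for futility" and adds: "Enrolment maybe stopped if the null hypothesis is rejected (efficacy) or accepted (futility) after the interim analysis". It also says that after an efficacy stop the second efficacy endpoint is tested at 1.613%. SAP Table 5 (section 5.3.1) gives the levels: "1-sided nominal type I error will be 1.61% at the interim analysis and 5.89% at the final analysis". It counts the objective as met when p is below the level for the analysis concerned. Protocol 10.3.3.1 has the same levels and criterion.

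**Passages that make the later analysis decisive.** SAP 7.1 says: "The main efficacy analysis and the respective conclusions on efficacy will be done on the total number of events, i.e. at 27 events". The next sentence of that bullet covers an early stop: "If the enrolment is stopped for efficacy or futility following the interim analysis and we do not observe planned number of 27 events" by the last subject's last visit, the analysis goes ahead on whatever events were collected. The table in SAP 7.1 lists the interim analysis as internal and the final analysis as the one for public disclosure and the study report. SAP 6 and Protocol 10.1.2 start the sequential procedure that leads to the second hypothesis only once the final analysis of the first is done.

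**The concern.** After an efficacy crossing, SAP 7.2 keeps subjects in follow-up until 12 months after the second dose, so events continue to accrue. The later analysis therefore uses more data than the interim and can give a different answer. In a group sequential design, a rejection at a binding efficacy boundary is final. Later data may revise the estimate but do not re-decide the test.

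SAP 7.1 attaches the efficacy conclusions to the later analysis and makes no exception for a trial that has already rejected. Enrolment could stop because efficacy was shown, and a report that followed SAP 7.1 to the letter could then state that it was not. The second hypothesis is touched as well: SAP 7.2 opens it at the interim, while SAP 6 and Protocol 10.1.2 open it only after the final analysis.

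**Working it through.** **Inputs from the documents**
- Overall design: "with an overall power equal to 80% and an overall one-sided alpha equal to 7.5"% (Protocol 10.1.2).
- Effect: "to observe an HR (hazard ratio) equal or below to 0.39" (Protocol 10.1.1).
- Looks: "with 48% and 100% of the total planned events" (Protocol 10.1.1), which are 13 and 27 events (SAP 7.1 and 7.2).
- Levels: 1.613% at the interim and 5.89% at the final analysis; SAP 7.2 ties 5.89% to 27 cases.

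**Assumptions.** Equal allocation (the first 40 or so proof-of-principle subjects are 3:1), normal log-rank statistics, and no stop for the non-binding futility rule. HR 0.7 is an illustrative weaker effect and is not in the documents.

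**1. Reproduce the plan's figures.** Classical O'Brien-Fleming boundaries are z1 = C/√t and z2 = C. With t = 0.48 and overall alpha 7.5%, C = 1.483 and z1 = 1.483/√0.48 = 2.141. This gives:
- interim alpha 1.613%, leaving 7.5% − 1.613% = 5.887%;
- interim and final beta 8.83% and 11.17%;
- 26.4 events in total, rounded up to 27, and 12.7 at the interim, rounded up to 13.

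The design reproduces.

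**2. Model for the two analyses.** With d events, Z has mean −ln(HR)·√d/2 and variance 1. The correlation between the looks is √(13/27) = 0.694. The thresholds are z = 2.141 (1.613%) and z = 1.564 (5.89%). At HR 0.39 the means are 0.9416 × √13/2 = 1.698 and 0.9416 × √27/2 = 2.446.

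**3. How often the two rules disagree.** Disagreement means Z1 > 2.141 and Z2 < 1.564, with 27 final events.

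| True HR | Cross at interim | Cross, then miss 5.89% | Share of crossings |
|---|---|---|---|
| 1 | 1.6% | 0.67% | 41% |
| 0.7 | 6.7% | 1.2% | 18% |
| 0.39 | 33% | 0.60% | 1.8% |

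**4. Error rates under each rule**

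| Rule | Type I error | Power at HR 0.39 |
|---|---|---|
| Only the 27-event analysis decides | 5.89% | 81.1% |
| Interim rejection stands, otherwise the final analysis decides | 6.56% | 81.7% |

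The second type I figure is 5.89% + 0.67%. Both are below 7.5%.

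**5. A concrete case.** Take 2 vaccine and 11 placebo events at the interim: z = (11 − 2)/√13 = 2.50, p = 0.006, rejected at 1.61%. If the next 14 events split 8 and 6, the total is 10 and 17: z = (17 − 10)/√27 = 1.35, p = 0.089, above 5.89%.

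**6. Fewer than 27 events.** No level is printed here. If 5.89% were carried over to 18 final events (an assumption), disagreement would be 0.28% of trials at HR 1, 0.55% at HR 0.7 and 0.52% at HR 0.39.

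**The case against.** The best defence is that SAP 7.1 describes only a trial that did not stop early. Its 27-event sentence ends with enrolment stopping at that point, which fits a trial still enrolling after the interim. The next sentence, on early stops, says only that an analysis proceeds. It does not say that the null hypothesis is re-tested or that an interim rejection is withdrawn. The binding boundary, the interim level in Table 5 and the test of the second endpoint at 1.613% all point to the interim rejection standing. SAP 7.3 adds that a statistic in the rejection region indicates that the efficacy criteria are met at the interim. The SAS code in SAP 5.3 is redacted and the decision-sequence figure is not shown; either might hold an explicit rule.

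Much of this stands. The documents lean towards the interim deciding, and a rule may exist out of sight. But SAP 7.1 does address the efficacy stop and exempts nothing. Its following bullet bars data beyond 27 events from the efficacy conclusion but places no such bar at an interim crossing. The visible text still needs reconciling.

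A reader might go further and infer that the sponsor may choose between the two results, or that the interim alpha buys nothing. The documents support neither: the efficacy boundary is declared binding, and stopping enrolment is a stated purpose of the interim analysis.

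**Conclusion.** The point holds as a conflict in wording with a small numerical effect. SAP 7.1, read literally, could overturn a valid interim rejection that SAP 7.2 and Table 5 treat as final. With 27 final events and the 5.89% level, this would happen in about 0.7% of trials at HR 1, 1.2% at HR 0.7 and 0.6% at HR 0.39. The share of interim rejections affected is 41%, 18% and 2%, but the 41% applies to crossings that occur in only 1.6% of null trials.

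Two stronger readings fail. Type I error is not inflated: it is 5.89% or 6.56% against an allowed 7.5%. And the documents do not assign 5.89% to every later analysis. It is printed for 27 cases, so figures for smaller event counts rest on carrying that level over. The results also rest on the normal approximation and equal allocation.

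**What to change.** In SAP 7.1, state: *If the efficacy boundary is crossed at the interim analysis, the first null hypothesis is rejected and this conclusion stands; the analysis at 27 events, or on all events at last subject last visit if fewer, then estimates VE only and is not a further test of the first hypothesis. Otherwise the conclusion is drawn at the final analysis.*

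In SAP 6, and in the matching sentence of Protocol 10.1.2, let the sequential procedure open after whichever analysis rejects the first hypothesis, as SAP 7.2 already provides. Table 5 and Protocol 10.3.3.1 need no change, because both already accept the interim level as sufficient.

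The cost is a few sentences, with no extra subjects, data or analyses. The one drawback is that a weaker later estimate may be reported beside a retained interim rejection.

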7.2. Statistical considerations for interim analyses

One interim analysis for efficacy and futility will be done following a group sequential design for the key secondary efficacy analysis. The interim analysis is event driven and is planned when 48% of the assumed total number of culture confirmed cases of recurrent *S. aureus* SSTIs (13 events after the second vaccination) will be observed and it may stop the enrolment of the study for efficacy or futility.

In case of stopping for efficacy at the interim analysis, also the second secondary efficacy endpoint will be tested with the same alpha used for the first hypothesis (alpha=1.613%). Enrolment maybe stopped if the null hypothesis is rejected (efficacy) or accepted (futility) after the interim analysis, but the follow up of subjects will continue for 12 months after the second dose.

The design assumes that 2 sequential tests are made for the key efficacy objective using test boundaries (binding for efficacy and not binding for futility) calculated by the O'Brien-Fleming spending function and assuming that time to event follows an exponential distribution. An adjusted alpha equal to 1.613 % and a beta equal to 8.83% (or a power equal to 91%) will be spent at the interim to reject or accept the null hypothesis for the key efficacy objective with a sample of 13 cases. At the final analysis the adjusted alpha and beta will be, respectively, 5.89% and 11.17% (or a power equal to 89%) with a sample of 27 cases. The final alpha and beta after the two sequential tests will be kept to 7.5% and 20%. The secondary efficacy endpoint will be tested at the final analysis after rejecting the null hypothesis for the key objective.

The proc SEQDESIGN is used for the planning of the test boundaries with the code reported in the section 5.3. The output with the limits is used in the proc SEQTEST (see section 5.3.2)

